t _{max}	time to reach maximum concentration
V _{ss}	the apparent volume of distribution at steady state calculated as: Dose/AUC x (AUMC/ AUC _{0-∞} - T/2) where T is the duration of intravenous injection
λ _z	the apparent terminal rate constant, estimated using the negative slope of the least square regression analysis of the log concentration versus time data for the terminal linear portion of the curve

Revision History

Document Version	Changes Made	Document Date
Draft 1	Draft specification based on the following documents: 
 • Study protocol VAL201-001 F2.0 • VAL201-001 CRF 	24 AUG 2015
Draft 2	Updated draft after amendment	08 JUL 2016
Final	Updated after Sponsor comments	24 AUG 2016
Amendment Draft 1.0	Updates following protocol amendment VAL201-001 version F5.0	29 JAN 2018
Amendment Draft 2.0	Updates following protocol amendment VAL201-001 version F6.0	17 JUN 2019
Amendment Final 2.0	Finalized Amendment version after Sponsor confirmation	05 SEP 2019
Amendment Draft 2.1	Updates following early study termination decision	10 FEB 2020
Amendment Draft 2.2	Updates following discussion with Sponsor	11 JUN 2020
Amendment Final 3.0	Finalized Amendment version after Sponsor confirmation	17 JUL 2020

Forms				
Title		Statistical Analysis Plan Template		
Code		Version	Effective Date	Page
FRM_ST03_032		01	23 Apr 2015	7 of 24

1. Introduction

The present Statistical Analysis Plan (SAP) outlines analysis to guide the programming for the data analyses of clinical study VAL201-001 protocol version F6.0 (last version - 7.0 - of study protocol was finalized and approved but never implemented for use in the study). The study was closed to further recruitment in January 2020 due to difficulty in recruiting patients to meet the inclusion/exclusion criteria within the current protocol; the treatment paradigm for patients had significantly evolved during the five years of patient recruitment being open. Any changes to the study protocol or Case Report Form (CRF) may necessitate updates to the SAP. In case of deviations from the finalized SAP, explanations will be provided in the clinical study report.

Relevant applicable CROS NT Standard Operating Procedures (SOP) will be followed in compliance with the agreement with the Client.

2. Study Objectives

The objectives of this clinical study are to assess the safety, tolerability, pharmacokinetics (PK) and activity of VAL201 in patients with incurable, locally advanced or metastatic prostate cancer. VAL201 may also be tested in patients with other advanced solid tumours. The inclusion of limited number of patients with other advanced solid tumours will confirm the MTD and assess preliminary anti-tumour activity.

2.1.1 Primary objective

The primary objective of this clinical study is to estimate the Maximum Tolerated Dose (MTD)/Maximum Administered Dose (MAD) of VAL201 in cancer patients with advanced solid tumors.

MTD refers to a dose with an acceptable and manageable safety profile, in the absence of the MTD
MAD refers to the highest dose level administered.

2.1.2 Secondary objectives

The secondary objectives of this clinical study are:

- To assess the safety and tolerability of VAL201.
- To evaluate the pharmacokinetics of VAL201.
- To assess anti-tumour activity of VAL201.

2.1.3 Exploratory objectives

This clinical study includes two exploratory objectives:

- To assess the pharmacodynamic (PD) activity of VAL201.
- To assess relevant tumour biomarkers.

Forms				
Title		Statistical Analysis Plan Template		
Code		Version	Effective Date	Page
FRM_ST03_032		01	23 Apr 2015	8 of 24

3. Study Design

3.1 General design and plan

This clinical study is designed to establish the MTD/MAD, safety, tolerability and PK of VAL201 by testing the drug (VAL201) on patients with incurable, locally advanced or metastatic prostate cancer and other advanced solid tumors. The design is a Phase I/II, open-label single-arm dose escalation study. The study design consists of a dose escalation part followed by an enrichment part. The study features includes: five cohorts of up to six patients, six cycles (main study) each cycle will last 21 days and an extended treatment period of VAL201 if a patient is considered suitable. Events that occur during each cycle will be considered for Dose Limiting Toxicity (DLT) assessment and therefore to establish the MTD/MAD.

The dose escalation will follow an accelerated enrolment of 3+3 design where the first two cohorts will enroll 1 patient each with an accelerated dose escalation schedule as described on Section 4.2 of the clinical study protocol (VAL201-001 version F6.0). Each patient will be followed up for AEs and DLT during each cycle. Where the Cohort Review Committee (CRC) suspects that drug-related events have occurred that merit further exploration at that dose level, they will request that the cohort 1 or 2 must enroll 3 more patients in order to thoroughly evaluate safety events prior to escalation. Cohorts of 3 patients will be enrolled from the 3rd cohort onwards (or earlier where the CRC recommend due to safety data evaluation). After a DLT has been identified the cohort will be expanded to 6 patients. If a second DLT is reported this will be declared the MTD.

The starting dose of VAL201 for the first cohort of patients will be 0.5 mg/kg/dose given on Days 1, 8 and 15 of each cycle. In the absence of DLT, the dose of VAL201 will be escalated for future cohorts in recommended increments according to the rules for dose escalation as described in Section 4.2 of clinical study protocol. All dose escalation decisions will be made by a CRC who shall convene to review all available safety data.

Intra-patient dose escalation will be adopted in Cohort 5; the CRC will evaluate the safety, clinical observations and PK data following cycle 1 (dosed at 8mg/kg) and approve escalation to 16 mg/kg on Cycle 4 Day 1. Based on the review of the safety data, the CRC may suggest an alternative dose regimen for the patient if required, to a maximum of 16 mg/kg. If a DLT occurs at 8 mg/kg requiring dose de-escalation, subsequent doses may be reduced. If a DLT occurs at 16 mg/kg, subsequent doses may also be reduced.

Cohort 6 will enroll a further 3 patients at a dose of up to 16 mg/kg; the dose will be decided upon by the CRC guided by safety, PK and PD data available from Cohort 5.

Once the MTD/MAD has been established for a given dose and schedule, up to 12 additional patients with incurable, locally advanced prostate cancer or other advanced solid tumors may be enrolled at this dose level (termed as “Enrichment Cohort”).

Thirty evaluable patients will be enrolled for the dose escalation part of the study and no more than 12 patients for the enrichment part of the study at the defined MTD/MAD for a total of 42 patients.

3.2 Visit Schedule and Visit Windows

The study design for the starting dose of VAL201 includes the following visit schedule and visit windows:

 cros nt	Forms			
	Title	Statistical Analysis Plan Template		
	Code	Version	Effective Date	Page
	FRM_ST03_032	01	23 Apr 2015	9 of 24

Window	Description	Visit window	
		Min (day)	Max (day)
Screening	Within 28 days of enrollment to Cycle 1 Day 1	-28	0
Cycle 1	Visits scheduled at Day 1, Day 2, Day 8, Day 9, Day 15	1	1
Cycle 2 - 5	Visits scheduled at Day 1 (Day 22 of the previous Cycle), Day 8, Day 15	1	1
Cycle 6	Visits scheduled at Day 1 (Day 22 of Cycle 5), Day 8, Day 15	1	1
Final Cycle Visit	This visit is performed one week after the final dose of VAL201 in any cycle	1	1
Final Study Visit	This visit is performed 30 days after the final dose of VAL201 in any cycle	5	5

Where the CRC recommend an adjustment to the dose schedule, the following visit schedule and visit windows will be performed:

Window	Description	Visit window	
		Min (day)	Max (day)
Screening	Within 28 days of enrollment to Cycle 1 Day 1		
Cycle 1	Visits scheduled at Day 1, Day 2, Day 8, Day 15	1	1
Cycle 2 - 5	Visits scheduled at Day 1 (Day 22 of the previous Cycle), Day 8, Day 15	1	1
Cycle 6	Visits scheduled at Day 1 (Day 22 of Cycle 5), Day 8, Day 15	1	1
Final Cycle Visit	This visit is performed one week after the final dose of VAL201 in any cycle	1	1
Final Study Visit	This visit is performed 30 days after the final dose of VAL201 in any cycle	5	5

Where a patient continues to receive VAL201 after completion of main study, the following visit schedule and visit windows will be performed:

Window	Description	Visit window	
		Min (day)	Max (day)
Cycle 7 onwards	Visits scheduled at Day 1 (Day 22 of Cycle 6), Day 8, Day 15	1	1
Final Study Visit	This visit is performed 30 days after the final dose of VAL201 in any cycle	5	5

Forms				
Title		Statistical Analysis Plan Template		
Code		Version	Effective Date	Page
FRM_ST03_032		01	23 Apr 2015	10 of 24

The activities that will be performed at each cycle and day are summarized in the protocol under SCHEDULE OF STUDY ASSESSMENTS (table i, table ii and table iii).

3.3 Sample size justification

Up to 42 patients with incurable, locally advanced or metastatic prostate cancer or other advanced solid tumours may be enrolled in this study. It will follow a dose escalation design, and the number of patients treated will therefore be dependent upon the number of dose levels investigated. A conventional algorithm (3+3 patients per dose level) will be used to identify the MTD or MAD, escalating on 0/3 or 1/6 DLTs, and de-escalating if 2 or more patients with DLTs are encountered. The MTD will be the highest dose level at which 0 of 3 or 1 of 6 patients experience a DLT, with the next higher dose having at least 2 of 3 or 2 of 6 patients experiencing a DLT.

The following table shows the operating characteristics of this 3+3 design. Under this design, there is a 71% chance of escalation if the true but unknown rate of DLT is 20% and less than 50% chance of escalation if the true but unknown rate of DLT is higher than 30%.

Operating characteristics of the 3+3 study design

True but Unknown Rate of DLT (%)	Probability of Escalation (%)
20	71
30	49
40	31
50	17
60	8

3.4 Assessment of the objectives

In the dose escalation phase, an exact 95% CI will be calculated for the response rate observed. No further formal statistical analysis will be performed. In the enrichment phase of the study the following assessment were planned to be performed:

3.4.1 Secondary objective assessment

- Evaluation of AEs during treatment and follow up.
- Assessment of pharmacokinetics measures.
- Tumor assessments following PCWG2 and RECIST 1.1 recommendations and may include the following as appropriate:
 - assessment of measurable and any selected non-measurable lesions by MRI scan (or CT if not possible) of chest, and abdomen/pelvis at Screening and on the completion of every 2 cycles (every 3 cycles in Cohorts 5 and 6);

Forms			
Title		Statistical Analysis Plan Template	
Code		Version	Effective Date
FRM_ST03_032		01	23 Apr 2015
		11 of 24	

- assessment of PSA levels in serum at screening and every 3 weeks (or at the end of each cycle);
- assessment of bone lesions by a whole-body radionuclide scan at Screening and on the completion of every 2-4 cycles (3 cycles in Cohorts 5 and 6);
- other assessments e.g. whole body MRI may be assessed as requested by investigator.
- percent change in PSA from baseline to tumour assessment time point;

$$\text{Percent change} = [1 - \exp(\ln(\text{PSA}_{\text{C}}/\text{PSA}_{\text{B}}))] * 100;$$

where:

PSAb is the PSA at the screening (day -28 to 0)

PSA_C is the PSA at day 1 of each cycle (x indicates the cycle 1 to 7 and onwards)

- maximum decline in PSA during study defined as the maximum reduction in PSA from the baseline (looking at all visits, following Cycle 1 Day 1, which is indeed Baseline Visit for PSA, up to the last final cycle visit or the last dosing visit, if final cycle visit is not present, inclusive); this value will be determined by the percent change in PSA from baseline, a negative percent will indicate a decline in PSA.
- based on the three pre-treatment PSA values, an estimate of pre-treatment PSA doubling time will be derived by regressing the natural log of the PSA values versus the time points, the slope of the regression will be used to estimate pre-treatment PSA doubling time

$$\ln(\text{PSA}) = a + bt_x$$

$$\text{doubling time: } \ln(2)/b$$

where \ln is the natural logarithm

a is the intercept,

b is the slope,

t_x are the time where the PSA test was performed.

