5.12 Tumour assessment prostate

Tumour assessment for prostate cancer patients will follow the PCWG2 guidelines or RECIST 1.1 guidelines and may include assessment of serum prostate-specific antigen (PSA) at screening and every 3 weeks or at the end of every cycle.

Forms				
Title		Statistical Analysis Plan Template		
Code		Version	Effective Date	Page
FRM_ST03_032		01	23 Apr 2015	19 of 24

A summary table for tumour assessment at screening and at each applicable cycle will be produced presenting descriptive statistics for longest tumour diameter (mm) reported as well as duration of tumour (years) and method of examination; longest tumour diameter will be classified by tumour location and such categories will be defined by a study medical expert reviewing the related information collected.

The assessment of prostate-specific antigen PSA outcomes will be summarised for each patient and time point including the percent change in PSA from baseline to tumour assessment time point.

An estimate of pre-treatment PSA doubling time will be presented in a summary table together with descriptive statistics for PSA values at each cycle and the related percent change from baseline.

Baseline PSA value is defined as the last available assessment before treatment start (which will be actually the PSA value collected at Cycle 1 Day 1).

Thereafter tumour assessment and prostate-specific antigen PSA assessment results will be listed, including also maximum decline in PSA during study.

If other methods were used to assess the tumour such CT scan or MRI then the results of the tests will be listed for each patient by time point.

6. Evaluation of objectives

The evaluation of the primary objective will be based on the safety set, the evaluation of the secondary objective will be based on the ITT set and the evaluation of the exploratory objective will be based on the ITT set and the PP set separately. Tables and listings will be presented separately.

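### The PSA percent-change formula is positive when PSA falls, while the SAP reads a negative percent as a decline; its screening baseline also conflicts with the Cycle 1 Day 1 baseline

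*SAP*

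**What the plan says.** Section 3.4.1 gives the SAP's only formula for PSA percent change. In the extracted text its right-hand side, after an opening bracket, reads "1 - \exp(\ln(\text{PSA}_{\text{C}}/\text{PSA}_{\text{B}}))] * 100". The legend below it defines the two terms:

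- Denominator: "PSAb is the PSA at the screening (day -28 to 0").
- Numerator: "PSA_C is the PSA at day 1 of each cycle (x indicates the cycle 1 to 7 and onwards").

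The next bullet defines maximum decline as the largest reduction from baseline and adds: "this value will be determined by the percent change in PSA from baseline, a negative percent will indicate a decline in PSA". It describes the visits to be searched as "looking at all visits, following Cycle 1 Day 1, which is indeed Baseline Visit for PSA", ending at the last final cycle visit or, if there is none, the last dosing visit.

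Section 5.12 has its own baseline rule, "Baseline PSA value is defined as the last available assessment before treatment start", and identifies that value as the Cycle 1 Day 1 one. It plans a summary table with "descriptive statistics for PSA values at each cycle and the related percent change from baseline", and a listing "including also maximum decline in PSA during study". It gives no formula.

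**The concern.** There are two conflicts.

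**Sign.** The formula and the rule for reading its result point in opposite directions. A programmer who follows both will label PSA rises as declines and declines as rises. If maximum decline is then taken as the most negative value, it picks the patient's PSA peak.

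**Baseline.** The legend divides by the screening value and counts Cycle 1 Day 1 among the follow-up values. The next bullet and section 5.12 make Cycle 1 Day 1 the baseline. In addition, the legend defines the numerator only at Day 1 of each cycle, so the percent change is undefined at any other visit that the maximum-decline search covers.

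Anti-tumour activity is a secondary objective. Only prostate cancer patients were included (section 6.2.3), and tumour biomarkers and the additional pharmacodynamic analyses were dropped (section 4.6). PSA is therefore one of the few activity readouts left. The outputs at stake are Tables 14.2-3.1 and 14.2-3.2 and Listing 16.2.6-1.

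**Working it through.** The SAP states no PSA figure, so there is no number of its own to reproduce. The check is algebra, followed by illustrative values that are not from the SAP.

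**Step 1: reduce the formula.** Because exp(ln(x)) = x, the formula equals 100 × (1 − PSA_C/PSA_B). It is positive exactly when PSA_C < PSA_B, that is, when PSA has fallen. This holds for any data.

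**Step 2: single values, baseline 20.**

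- PSA 10: 100 × (1 − 10/20) = +50. This is a halving, but reads as a rise.
- PSA 40: 100 × (1 − 40/20) = −100. This is a doubling, but reads as a 100% decline.

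**Step 3: maximum decline, baseline 20.**

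| PSA | SAP formula | (PSA_C/PSA_B − 1) × 100 |
|---|---|---|
| 16 | +20 | −20 |
| 12 | +40 | −40 |
| 18 | +10 | −10 |
| 30 | −50 | +50 |

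Under the SAP formula the most negative value is −50, at the peak of 30. The true maximum decline is 40%, at the value of 12. The form in the last column agrees with the SAP's reading rule.

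**Step 4: can the two baselines be read as one?** No. The screening window ends at day 0, and the legend treats Cycle 1 Day 1 as a follow-up value. With Cycle 1 Day 1 as baseline, its own percent change would be zero by construction.

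**Step 5: size of the baseline effect.** The SAP gives neither the actual gap between the two samples nor the PSA growth rate. Assume a gap of 7 to 28 days, a doubling time of 3 to 12 months and a month of 30.44 days. The growth factor between the samples is g = 2^(gap/doubling time):

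| Gap | Doubling 3 months | 6 months | 12 months |
|---|---|---|---|
| 7 days | 5.5% | 2.7% | 1.3% |
| 14 days | 11.2% | 5.5% | 2.7% |
| 28 days | 23.7% | 11.2% | 5.5% |

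With the sign corrected, a true −30% from Cycle 1 Day 1 reads as 100 × (0.7g − 1) from screening. That is −29.1% for 7 days and 12 months, and −13.4% for 28 days and 3 months.

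The direction reverses only when the true decline is smaller than 100 × (1 − 1/g), which runs from 1.3% to 19.1% over the same range. For example, with screening 80, Cycle 1 Day 1 100 and a later value of 90, the change is +12.5% from screening and −10% from Cycle 1 Day 1.

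**The case against.** **The formula may no longer be in use.** Section 3.4 introduces the list as enrichment-phase assessments, and section 4.6 drops the enrichment analysis. This does not dispose of the point. Section 6.2.3 sends the PSA analysis to section 5.12, which still plans percent change and maximum decline without a formula of its own. Section 5.12 does not cite 3.4.1 either, so continued use is an inference, but 3.4.1 has the only formula a programmer can find.

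**The reversal needs a selection step that the SAP does not state.** Maximum decline is worded as the largest reduction, not as the most negative value. A programmer who followed the words would choose the right visit and could only print the wrong sign. PSA values are tabulated beside the percent change, and a PSA that more than doubles would give a value below −100%, impossible as a decline. All of this stands: a reversed result is possible, not certain.

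**The intended baseline is clear.** Two consistent statements name Cycle 1 Day 1, against one legend. That is fair as to intent, but the legend belongs to the formula itself and still has to be changed.

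**By-cycle summaries and a best value over all visits may properly use different visits.** Agreed. What needs repair is only that the legend does not define the percent change at the other visits.

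**The gap and doubling time are assumptions.** They are. A shorter gap or a stable PSA would bring the baseline effect close to zero, and a falling PSA would reverse its direction.

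A subscript may have been lost when the PDF was read, but that cannot turn a ratio minus one into one minus a ratio.

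**Conclusion.** The concern holds. The sign conflict is certain, rests on algebra alone and is not corrected anywhere in the SAP. Followed literally, the formula and the reading rule invert the direction of every non-zero PSA change.

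The baseline conflict is also explicit in the text, but secondary. It changes the size of the reported change and only sometimes its direction; its numerical size depends wholly on the assumed gap and doubling time.

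The consequence is limited to descriptive secondary activity outputs. Response rate rests on the PCWG2 questions in the CRF (section 4.5) and MTD/MAD on DLTs (section 6.1), and neither uses this formula. This should be fixed before the PSA outputs are programmed or, if they already exist, checked against the code.

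**What to change.** 1. In section 3.4.1, replace the formula with Percent change = (PSA_C/PSA_B − 1) × 100, which matches the existing rule that negative means decline. Keeping the formula and stating that positive means decline would also work, if done throughout.
2. Define PSA_B once, as the last pre-dose value (Cycle 1 Day 1), in line with section 5.12.
3. Report percent change by cycle from Cycle 2 Day 1 onwards.
4. Define maximum decline as the minimum percent change over all visits after Cycle 1 Day 1, up to and including the final cycle visit or, if absent, the last dosing visit, as 3.4.1 already lists. Let PSA_C cover those visits.
5. State that a positive minimum means no decline was observed. This is a clarification for the listing, not needed to resolve the conflict.

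The cost is a few lines of SAP text and the matching program lines. No new data are needed.

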3.4.2 Exploratory objective assessment

- Assessment of pharmacodynamics activity of VAL201.
- Assessment of tumour biomarkers.

3.5 Safety endpoints

The safety analysis will include all patients screened and enrolled for whom has been given at least one dose by subcutaneous (s.c.) injection of VAL201.

The number and percent of subjects experiencing Adverse Events (AEs) will be reported by dose. In addition the incidence of AE and suspected DLTs will be graded according to the Common Terminology Criteria for AEs (CTCAE), version 4.03.

In order to assess the primary objective of the analysis the following classification of the safety variables will be apply:

Forms				
Title		Statistical Analysis Plan Template		
Code		Version	Effective Date	Page
FRM_ST03_032		01	23 Apr 2015	12 of 24

Dose Limiting Toxicity (DLT)

A DLT is defined as a drug –related Grade 3 or 4 AE (from CTCAE version 4.03) that, in the opinion of the Investigator and/or CRC, represents a clinically significant hazard to the patient; a list of exceptions is presented in Section 4.2.1 of the study protocol.

DLT events will also be considered in terms of:

- inability to administer the planned Cycle 1 dose administration schedule;
- clinically significant toxicity events considered related to VAL201 which lead to a dose delay of more than 7 days during Cycle 1.

Pre-treatment adverse events-

An AE will be classified as pre-treatment AE if it starts before the date/time of day of first medication intake in the study.

Treatment-emergent adverse event (TEAE)

An AE will be classified as a TEAE if it starts on or after the date/time of day 1 cycle 1 of the study. In case of missing or incomplete dates/times not allowing a direct allocation to any of the two categories of AEs, it will be considered to be treatment-emergent, unless the stop date is known to be prior to the first administration of the study medication. The AE will be allocated to the first category allowed by the available data, according to the following order:

- TEAE
- Pre-treatment.

Serious adverse event (SAE)

A SAE is an AE judged as serious.

Adverse Event Related to study drug

An AE is considered as related to study drug if it is judged as “Possibly Related”, “Probably Related” or “Definitely Related” or with missing relationship.

Adverse event leading to death

Every adverse event (AE) including serious adverse event (SAE) is recorded and graded for severity according to the CTCAE v4.03. An adverse event (AE), including a serious adverse event (SAE), with a severity outcome equal to “Death related to AE” (Grade 5 from CTCAE version 4.03) is by definition an adverse event leading to death.

Count of adverse events

Two AEs with the same Preferred Term (PT) and classified in the same category (pre-treatment AE or TEAE) will be considered as two different events when calculating the “number of events” in the tables, unless they have same onset time and date.

Forms				
Title		Statistical Analysis Plan Template		
Code		Version	Effective Date	Page
FRM_ST03_032		01	23 Apr 2015	13 of 24

4. Statistical Analysis

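### The DLT definition in SAP section 3.5 stops at Grade 4, so read literally a drug-related death in Cycle 2 or later is not counted as a DLT.

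*SAP*

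**What the plan says.** Section 3.5 of the SAP sets out the safety classifications used for the primary objective. Its grade-based DLT criterion is a drug-related "Grade 3 or 4 AE (from CTCAE version 4.03") that the Investigator and/or CRC regards as a clinically significant hazard. Protocol section 4.2.1 is cited there only for a list of exceptions.

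Two further criteria follow. One is "inability to administer the planned Cycle 1 dose administration schedule". The other is clinically significant toxicity, related to VAL201, that would "lead to a dose delay of more than 7 days during Cycle 1".

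Grade 5 appears later in the same section, in the definition of an AE leading to death: "Grade 5 from CTCAE version 4.03) is by definition an adverse event leading to death". That definition is not linked to DLT.

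Sections 3.1 and 4.6 state that DLTs are assessed in every cycle, and section 3.1 adds that this assessment serves to establish the MTD/MAD. For Cohort 5, section 3.1 has the CRC "approve escalation to 16 mg/kg on Cycle 4 Day 1", and it foresees DLTs at that dose: "If a DLT occurs at 16 mg/kg, subsequent doses may also be reduced".

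**The concern.** The definition leaves out the most severe grade. The Cycle 1 criteria have no grade limit and would catch a death that prevents a planned Cycle 1 dose, but they have no counterpart for later cycles. Section 4.6 records that DLT follow-up was extended from the first cycle to all cycles, while these two criteria still refer to Cycle 1 only.

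The gap is widest for Cohort 5 at 16 mg/kg. That exposure starts three cycles after the Cycle 1 criteria have lapsed, so only the Grade 3 or 4 criterion can apply there.

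At stake is the DLT count by cohort in Table 14.2-1, and with it whether the report names an MTD or, in its absence, a MAD (section 2.1.1).

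**Working it through.** **1. The plan's own figures.** Section 3.3 tabulates the probability of escalation under 3+3. With true DLT rate p, P = (1−p)³ + 3p(1−p)² × (1−p)³.

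- p = 0.20: 0.512 + 0.384 × 0.512 = 0.709 (stated 71%)
- p = 0.30: 0.343 + 0.441 × 0.343 = 0.494 (stated 49%)
- p = 0.40: 0.216 + 0.432 × 0.216 = 0.309 (stated 31%)
- p = 0.50: 0.125 + 0.375 × 0.125 = 0.172 (stated 17%)
- p = 0.60: 0.064 + 0.288 × 0.064 = 0.082 (stated 8%)

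The table is correct. The question is which events count towards p, not the arithmetic.

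**2. Events set against the three criteria of section 3.5.**

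| Drug-related event | Grade criterion | Cycle 1 schedule | Cycle 1 delay | DLT as written |
|---|---|---|---|---|
| Grade 3 or 4, any cycle, judged a hazard, no exception | met | not needed | not needed | yes |
| Grade 5 in Cycle 1, before the planned doses are complete | not met | met | not needed | yes |
| Grade 5 in Cycle 1, after the Day 15 dose | not met | not met | arguable | unclear; not claimed here |
| Grade 5 in Cycle 2 or later | not met | cannot apply | cannot apply | no |

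The last row is the gap. It assumes that the event was not also recorded at Grade 3 or 4 before death.

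**3. Planned exposure in Cohort 5.** Six main-study cycles with dosing on Days 1, 8 and 15 give 6 × 3 = 18 doses. Cycles 4 to 6 give 3 × 3 = 9. If the CRC approves 16 mg/kg as planned, 9 of 18 main-study doses, and every one of them at 16 mg/kg, fall where neither Cycle 1 criterion can apply. This describes the schedule and is not an effect size.

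**4. Effect on the count, given one such death.** Section 3.3 works by "escalating on 0/3 or 1/6 DLTs, and de-escalating if 2 or more patients with DLTs are encountered". Section 3.1 adds: "After a DLT has been identified the cohort will be expanded to 6 patients". Sections 3.1 and 6.1 declare the MTD at a second DLT.

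- Cohort of 3, no other DLT: counted 0/3 = 0%; with the death 1/3 = 33%. A count of 1/3 calls for expansion to six. It does not by itself set an MTD.
- Cohort of 6, one Grade 3 or 4 DLT in another patient: counted 1/6 = 17%; with the death 2/6 = 33%. At 1/6 the dose passes. At 2/6 it leads to de-escalation under section 3.3, or is a second DLT under sections 3.1 and 6.1. The reading of the MTD/MAD changes under either rule.

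**5. Which decisions are exposed.** Section 6.1 ties permission to escalate to CRC review at the end of Cycle 1, so a death in Cycle 2 or later would often come after that decision. Section 1 states that recruitment closed in January 2020, and this SAP version was finalised in July 2020. What remains exposed is the final count and the MTD/MAD drawn from it.

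**The case against.** **The protocol may cover deaths.** It is not at hand, and a DLT definition is ordinarily protocol content. However, the SAP restates the definition in its own words and cites section 4.2.1 only for exceptions, which narrow it. The objection justifies checking protocol F6.0 first. It does not remove the gap in the SAP.

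**A clinical judgement would catch it.** DLT status rests partly on the opinion of the Investigator and/or CRC, and the SAP does not say that Table 14.2-1 is programmed from grade alone. The CRC would very likely treat a drug-related death as dose-limiting. This stands as far as live decisions go. As written, though, the hazard judgement qualifies Grade 3 or 4 events and does not extend the definition to Grade 5.

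**Deaths stay visible.** AEs leading to death are summarised (section 6.2.1) and serious TEAEs are listed (Listing 16.2.7-2.2), so a death would not vanish from the report. It would be shown as a death and not as a DLT. Section 7.2.2 names no separate DLT listing in which the mismatch would show.

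**A reader might infer that the gap made escalation more likely.** That would need a rate of fatal toxicity, which the documents do not give, and escalation decisions that turned on events after Cycle 1. Section 6.1 places those decisions at the end of Cycle 1, so no change in the escalation probabilities is claimed.

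**Conclusion.** The point holds as a gap in a stated definition. Taken literally, section 3.5 counts a drug-related Grade 3 event in Cycle 2 or later but not a drug-related death in the same cycle, including any at 16 mg/kg in Cohort 5.

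Its size is conditional. If such a death occurred, the count for its cohort is one too low. The MTD/MAD reading changes only when that death is a second DLT in its cohort, as with 1/6 in place of 2/6. A lone death in a cohort of three moves the count from 0/3 to 1/3 and no further.

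Three stronger readings are not supported:

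- *That one omitted death turns an MTD into a MAD.* One DLT in three triggers expansion, not an MTD.
- *That DLTs after Cycle 1 are ignored altogether.* The Grade 3 or 4 criterion has no cycle limit.
- *That a death was in fact missed.* The SAP reports none. As it is not a results document, its silence settles nothing either way.

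The conclusion assumes that the definition is applied as written, that protocol F6.0 adds nothing on Grade 5, and that the fatal event has no earlier Grade 3 or 4 record that would itself count as a DLT.

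**What to change.** First check the DLT definition in protocol F6.0. Then change the grade criterion in section 3.5 to *drug-related Grade 3 or higher AE*, with the hazard judgement and the section 4.2.1 exceptions applying to Grades 3 and 4 only. Count a Grade 5 event in any cycle as a DLT in Table 14.2-1 when the Investigator and/or CRC judges it drug-related.

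Section 3.5 also treats an AE with a missing relationship as related. For a fatal event this should not create a DLT automatically; the CRC should resolve the relationship. Any difference from the protocol should be recorded in the clinical study report, in line with section 1 on deviations.

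The cost is one sentence, one comparison with the protocol, and one check of fatal events. The table in section 3.3 is unchanged, because it is expressed in terms of the true DLT rate. The downside is a small change to the safety definition after recruitment closed, possibly differing from the rule the CRC applied, which is why the difference needs to be reported.
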